We also tested an alternative dosing strategy in an effort to counteract these PK changes and demonstrated that obese women taking double the approved LNG EC dose normalized the PK profile to that of normal BMI women. Although a “take two” strategy could be rapidly implemented into clinical practice, we have no data on the resulting end-organ effects. Further studies are needed to document if PK normalization results in improved pharmacodynamic (PD) outcomes. Another alternative treatment strategy is to use a UPA-based EC instead. UPA is slightly more effective than LNG-based EC as it has a longer window of action (e.g. effective until LH peak vs. LH rise) [2]. However, published data demonstrate a possible decline in efficacy for obese women [4]. Detailed PK and PD studies for UPA have yet to have been performed in obese women but unpublished data from a colleague at Columbia University also demonstrated PK differences (*personal communication 4-2016*).

The overall goal of this research is to improve EC effectiveness and quality of clinical care for obese women. We hypothesize that increasing the dose of LNG- and UPA-based EC will normalize PK (specifically the time needed to reach a therapeutic drug level) and PD outcomes (follicle rupture) in obese women who weigh 80kg or greater. In this application we propose to expand our model for LNG- to UPA-based EC, assess the pharmacodynamic outcomes of these alternative dosing regimens (“take two”) in obese women and to assess the safety and acceptability of these regimens in this population.

Methods:

Study design: This is a 2-part study: Part 1 will be focused on LNG-EC and Part 2 will be focused on UPA-EC. Eligible women can take part in both aspects of the study and in no particular order. If they do choose to enroll

in both aspects of the study, then the screening visit does not need to be repeated unless it has been greater than 12 months since the original screening visit.

Part 1 LNG-EC is a randomized control trial. Part 2 UPA-EC is a randomized cross-over study with an additional non-randomized control arm.

This study will be conducted at Oregon Health & Science University (OHSU) in Portland, OR and a subcontract site, Eastern Virginia Medical School (EVMS) in Norfolk, Virginia. EVMS will be overseen by their own IRB.

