PK parameter analysis. UPA PK parameters will be generated by noncompartmental methods using WinNonLin (Pharsight, Mountain View, CA). Cmax and time to maximum Cmax will be observed values. Area under the curve (AUC) will be calculated from Time 0 to 120hr (AUC0-120) using the linear trapezoidal rule and then extrapolated to infinity which provide a more accurate calculation of drug clearance (Rowland 1980). Drug half-life (t1/2), oral clearance (CL), and volume of distribution (VD) will be generated using standard pharmacokinetic calculations ($t_{1/2} = 0.693/\lambda_z$ where λ_z is the terminal elimination rate constant; $CL = dose/AUC_{0-\infty}$; $VD = CL/\lambda_z$). Descriptive statistics will be generated for each parameter [mean (standard deviation)], concentration-time curves will be generated for all of the doses and their respective BMI groups. Depending on the normality of the data, parametric or nonparametric testing will be performed for each parameter between the normal and obese BMI ECx1 groups and paired statistics will be utilized to compare obese BMI ECx1 and ECx2.

We also plan to perform analyses to compare PD outcomes in obese users ingesting LNG and UPA, ECx1 and ECx2. UPA and LNG are the only two orally-dosed EC agents available on the market. A logical sub analysis is the comparison of the different dosing strategies to help guide future studies or even clinical management of orally-dosed EC in obese women if dose escalation appears effective. We will utilize the data collected in Aim 1 and 2. The proportion of women with a delay in follicular rupture (yes/no) in 4 different treatment regimens obtained in the trial in aim1 and 2 will be compared and test if there's significant difference

between LNG ECx2 and UPA LNG ECx2 using Chi-square test. Due to exploratory purpose of these analyses, the analysis will be descriptive but given the projected sample size (35 per group in Part 1 and 80 per group in Part 2) we will achieve more than 80% power with 5% of significance level to detect 23% difference in delay in follicular rupture. In addition, one of the secondary outcomes of time from treatment intake to follicular rupture will be compared among treatment groups using survival analysis.

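### The UPA pharmacokinetic (PK) plan picks a test per parameter from an undefined normality check and commits to no exposure ratio or confidence interval

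*Combined protocol and SAP*

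**What the plan says.** The Part 2 paragraph on PK parameter analysis (combined protocol and SAP) takes Cmax and its time from the data ("Cmax and time to maximum Cmax will be observed values"). It computes AUC to 120 hours and to infinity, and then: "Drug half-life (t1/2), oral clearance (CL), and volume of distribution (VD) will be generated using standard pharmacokinetic calculations".

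The summary is arithmetic: "Descriptive statistics will be generated for each parameter [mean (standard deviation". The test is then chosen from the data: "Depending on the normality of the data, parametric or nonparametric testing will be performed for each parameter". That clause applies to the comparison "between the normal and obese BMI ECx1 groups". For the two doses within obese women the text says only that "paired statistics will be utilized to compare obese BMI ECx1 and ECx2".

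The documents mention no log transformation, geometric mean, ratio, CI or PK significance level. They name no normality test and no range that would count as normalized.

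Specific Aim 2 is to compare UPA PK and pharmacodynamics between obese and normal BMI women and to see whether a higher dose helps. The Part 2 hypothesis is that peak level is lower in obese women. The overall goal in the Background is that raising the dose "will normalize PK (specifically the time needed to reach a therapeutic drug level").

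**The concern.** Whether obese women have lower exposure, by how much, and how much of the gap a double dose closes are questions of size. The Background itself reports the preliminary levonorgestrel result that way, as a Cmax 50% lower. A p-value from a t-test or rank test does not answer them, and an arithmetic mean with SD is a poor summary if the data are right-skewed, as concentrations usually are.

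Because the choice is made for each parameter, Cmax and AUC, two measures of the same exposure, may be compared on different scales in one report. One could be a difference in means and the other a rank comparison. Someone reading the paper could not set them side by side, or against published normal-BMI values.

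The comparison that bears most directly on normalization, obese women on ECx2 against normal-BMI women on ECx1, is not among the planned PK comparisons.

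**Working it through.** **Inputs from the documents.** Full PK sampling in 30 obese women in both cycles, and in the normal-BMI controls in one cycle (Part 2 UPA-EC). Controls: target 10, with 12 enrolled. The control number is described as a convenience sample (Part 2, Data Analysis & Sample Size). There is no PK sample size, power or CV, so there is no PK figure to reproduce.

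**Assumptions.** Lognormal data; between-woman CV 30% to 60% unless stated; within-woman CV 20% to 40%; the check is Shapiro-Wilk at 5% on untransformed values, with failure leading to a rank test. The plan states none of these.

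**1. How often the check switches test.** Simulating 30 v 10 or 12 women, with failure in either group leading to Mann-Whitney, the rank test is chosen in about 42-46% of trials at CV 30%, 59-63% at 40%, 74-76% at 50% and 85-87% at 60%. If Cmax and AUC have a log-scale correlation of 0.7 (assumed; 30 v 12), they receive different tests in about 40% of trials at CV 30% or 40%, and about 31% at 50%.

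**2. Error rates, unpaired.** At a true ratio of 1, the two-stage rule rejects in 4.6-5.8% of trials and a log-scale t-test in 4.6-5.1%. Power, two-stage v log-scale:

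- 30 v 12, CV 40%, ratio 0.7: 75.0% v 74.2%
- 30 v 10, CV 50%, ratio 0.7: 51.0% v 52.8%
- 30 v 10, CV 80%, ratio 0.6: 46.7% v 49.7%

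The gain runs from about -1 to +3 points.

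**3. Power, paired (30 women).** The plan does not say that the check applies here; suppose it does, on the within-woman differences. Over between-woman CV 40% or 60% and within-woman CV 20-40%, the log-scale paired t-test gains about 3 to 8 points at ratios of 1.2 to 1.3, except where power is already near 100%. Examples at within-woman CV 30%, ratio 1.2: 59.4% v 64.5% (between-woman CV 40%) and 57.1% v 64.8% (60%). At a ratio of 2, every method has about 100% power. The p-value then says little and the ratio is the useful result.

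**4. What the ratio would show.** Log-scale SD s = sqrt(ln(1 + CV²)).

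- *Unpaired, CV 50%:* s = sqrt(ln 1.25) = 0.472. SE = s × sqrt(1/10 + 1/30) = 0.1725, with t = 1.686 on 38 df. The 90% CI at a true ratio of 1 is exp(±0.291) = 0.75 to 1.34. With 12 controls, SE = 0.1613 and the CI is 0.76 to 1.31. The 95% CIs are 0.71 to 1.42 and 0.72 to 1.39.
- *Over CV 30% to 60%:* with 10 controls the 90% CI goes from 0.83-1.20 to 0.71-1.41.
- *A missed deficit, CV 50%:* for a true ratio of 0.75, |ln 0.75|/SE = 0.288/0.1725 = 1.67 (10 controls) or 0.288/0.1613 = 1.78 (12). Noncentral-t power is about 37% or 41%, so about 60% of trials would find no significant difference.
- *Paired, within-woman CV 30%:* s = sqrt(ln 1.09) = 0.294. SE = s × sqrt(2/30) = 0.0758, with t = 2.045 on 29 df. A true ratio of 2 has a 95% CI of 2 × exp(±0.155) = 1.71 to 2.34.

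**The case against.** The strongest reply is that nothing is broken. Error rates hold and unpaired power hardly moves. The primary test is McNemar's on delayed follicular rupture, and the controls serve mainly to check findings against published values. On this view, asking for ratios is a matter of taste. The part about error rates stands. It does not answer the reporting gap, because PK is part of a specific aim and the plan commits to no effect size for it.

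Four stronger readings are tempting, and the documents do not support them:

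- *That testing is on raw values.* The text refers only to the normality of the data, and a t-test on logs is also parametric. The arithmetic summary and the absence of any transformation make raw values the natural reading, but it is an inference.
- *That the check governs both comparisons.* The clause is attached to normal v obese at ECx1. The paired test is simply unspecified.
- *That the choice of test is largely chance.* This fits moderate CVs. At CV 60% the rank test is chosen about 86% of the time, which is close to a fixed outcome.
- *That normalization is defined as an exposure ratio.* The Background glosses it as a time measure, and the Part 2 hypothesis on peak level is directional, so a two-group test does address it. The ratio argument applies to Cmax, AUC, CL, VD and half-life, not to time to Cmax.

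**Conclusion.** The point holds as a gap in specification and reporting. The normality criterion and scale are undefined, the paired test is unnamed, the direct normalization contrast is absent, and no exposure ratio or CI is promised. A reader might infer inflated type I error or a material loss of power from the data-driven choice. The simulations show neither for the unpaired comparison. The gain from changing is one interpretable estimate per parameter, plus some efficiency in the paired comparison if the true ratio is modest.

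The practical risk is a non-significant difference against 10 to 12 controls being read as normalization, when the interval could still run from about 0.75 to 1.34. That range and the simulated figures rest on assumed CVs, lognormal data and an assumed Shapiro-Wilk rule. The absence of a ratio or CI does not depend on them. This is a worthwhile improvement and does not threaten the primary analysis.

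**What to change.** Replace the normality-based choice in the PK parameter analysis with a prespecified log-scale analysis of Cmax, AUC0-120, AUC0-infinity, CL, VD and half-life. Report geometric means, and geometric mean ratios with 95% CIs, for:

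- (a) obese v normal BMI at ECx1, as a two-sample comparison on logs;
- (b) obese ECx2 v ECx1, as a paired analysis on logs;
- (c) obese ECx2 v normal ECx1, the direct normalization contrast.

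Analyse time to Cmax by a named nonparametric method. State that a non-significant result in (a) or (c) will not be taken as evidence of similarity, and preferably state beforehand what ratio range would count as normalized.

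Include a period term in (b) only if dose order is randomized. Part 2 calls the study a randomized cross-over, but also describes obese women taking the standard dose in the first treatment cycle and the double dose in the second. Read literally, the second description leaves period and dose inseparable. The two descriptions must be reconciled before the model is fixed.

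The cost is analysis-plan wording, with no new participants, samples or visits.

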Rationale: Dose escalation is a commonly used strategy in pharmacotherapeutics [16]. We have already tested this strategy in our preliminary studies and demonstrated that we can normalize the LNG peak level in obese women by doubling the dose. It remains unknown if this improved drug level will translate into better end-organ suppression. However, we have had prior success with improved end organ suppression with dose escalation in our studies of oral contraceptives in obese women [11] thus we have confidence in this strategy for EC. The findings of our proposed studies, whether positive or negative, will provide critical information as we will have either proven or disproven if this potential solution works.

Part 1 LNG-EC:

The study flow for Part 1 is depicted in the graphic below. Part 1 will be performed as an open-label randomized control trial. Randomization will occur in a 1:1 fashion utilizing a computer generated random

permuted block randomization scheme with block size 4, 6 and 8.

Demographic information will be obtained including but not limited to race, ethnicity, parity, and prior contraceptive use. After

confirmation of ovulation via an elevated P4 of 3ng/mL or greater in the screening cycle.

Subjects will be randomized to treatment group [LNG-EC 1.5 mg (ECx1) or LNG-EC 3mg (ECx2)] and undergo a treatment cycle.

During the treatment cycle, subjects will undergo every other day visits starting on cycle day 6-8 followed by daily visits for up to 7 days once a dominant follicle measuring 15mm or greater in one diameter is visualized (see procedure flow below). Daily visits will cease prior to 7 days if evidence of follicle rupture (disappearance of or greater than 50% reduction in size of the dominant follicle) occurs. At each visit, subjects will undergo blood sampling via a single venipuncture for P4, E2 and LH levels and high-resolution transvaginal ultrasonography (TUS) (GE Ultrasound OR, 9900 Innovation, Voluson eBT11) to monitor follicular development and evidence of ovulation.

During the treatment cycle, study medication will be dosed on the day a ≥ 15 mm follicle is visualized. Women will be randomized to either LNG ECx1 (1.5mg LNG) or LNG ECx2 (3mg LNG). Study medications will be given by study staff and ingestion will be directly observed. Prior to ingesting study medication, women will undergo urine pregnancy testing to confirm non-pregnant status.

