Study end will be at the onset of menses at the end of the treatment cycle (defined as two consecutive days of spotting/bleeding). We estimate up to 12 visits in the treatment cycles depending if delay in ovulation occurs. Subjects will have the option to undergo a washout cycle and participate in the studies detailed in Part 2; if they chose to do so, they will not have to undergo another screening visit or control cycle.

Procedure flow:

	Visit 0 (Screening Visit)	Treatment Cycle Starting Cycle 1 day 6-8
Consent, Screening tests and medical history	X	
blood draws	X	X
ultrasound		X
Study Medication & urine pregnancy test		X*
Total time	2 hour	30 min/visit

*Visit number study medication will be taken depends on ultrasound findings.

Data Analysis & Sample Size: All analyses will be performed on an intention-to-treat (ITT) basis. To demonstrate equality between treatment arms at baseline, we will compare participant demographics using two sample t-test or chi-square test, and descriptive statistics such as mean, median and percentages within each group will be reported. **The primary outcome analysis will compare the proportion of women with no follicular rupture (yes/no) between the treatment groups using a Chi-square test.** As mentioned previously, follicle rupture will be defined as the disappearance of or $>50\%$ reduction of size of the leading follicle [2,17].

Confirmation of the timing of ovulation will be supported by LH, P4, and E2 levels. If necessary, we will address any unanticipated imbalances between the treatment groups after randomization by adjusting for these confounders in analysis using a logistic regression. Descriptive statistics will be utilized to report LH and P levels [mean (standard deviation)], follicular diameter [median (range)], and cycle day [median (range)] on the day of EC ingestion during the treatment cycle within each group. Additionally, the proportion of inhibition of follicular rupture by LH status (no surge, start of LH surge, or after LH peak) [2,17] for each cycle will be compared between treatment groups using fisher's exact test. Mean LH, P4, and E2 levels over time will be plotted by treatment group. Time from treatment intake to follicular rupture will be assessed by a survival

analysis using Kaplan-Meier curve and log-rank test. All statistical analyses will be performed with the SAS version 9.4 (Cary, NC, USA).

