(TUS). The TUS will be performed using a high-resolution transvaginal ultrasonography (GE Ultrasound OR, 9900 Innovation, Voluson eBT11) to monitor follicular development and evidence of ovulation. During the treatment cycles, study medication will be dosed on the day a 15 mm follicle is visualized. Both the normal and obese BMI groups will undergo treatment cycle 1 and receive a standard dose of UPA EC (30mg) or ECx1. After at least one washout cycle, only the obese group will complete treatment cycle 2 and receive a double dose of UPA EC (60mg). Study medications will be given by study staff and ingestion will be directly observed. Prior to ingesting study medication in each treatment cycle, women will undergo urine pregnancy testing. Study end will be at the onset of menses at the end of the treatment cycle (defined as two consecutive days of spotting/bleeding). We estimate that approximately up to 12 visits in the treatment cycles depending if delay in ovulation occurs.

During each treatment cycle, PK parameters will be obtained via serum samples through an indwelling catheter. IV placement in obese women can be challenging. We will enlist the assistance of OHSU's NIH funded CTSA nursing staff or IV therapy, if necessary, to place IVs in our obese cohort in order to ensure the least traumatic process for our subjects. We plan to obtain samples at 0.5, 1, 1.5, 2, 3, 4, 24, 48, 72, 96, and 120 hours for our normal controls in treatment cycle 1 and a subset of the obese cohort (n=30) in both treatment cycle 1 and 2. The IV will be left in place for the closely spaced samples and then single samples via phlebotomy will be obtained on the samples timed at 24 hours and later. This extended sampling scheme will allow us to determine a more accurate area under the curve by having observed rather than estimated values. Furthermore a prolonged sampling scheme will enable estimation of additional PK parameters that can lead to mechanistic insights.

Of note, Eastern Virginia Medical School will not be recruiting or enrolling participants for the Part 2 – UPA Normal BMI cohort as enrollment of the 12 participants for this group is complete.

Procedure flow for obese BMI study groups

	Screening Visit (1 visit)	Treatment Cycle 1 Starting Cycle day 6-8 (up to 12 visits)	Washout Cycle 2 (no visits)	Treatment Cycle 3 Starting Cycle day 6-8 (up to 12 visits)
Consent, Screening tests and medical history	X			
Phone or email contact			X	
Blood draws	X	X		X

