A sample size of 73 will achieve 80% power to detect a 20% difference in the proportion of cycles that demonstrate at a delay in follicular rupture (yes/no) using a two-sided McNemar test with a Bonferroni-adjusted 2.5% significant level. We estimate that 40 women will choose to participate in Aim 2 after completing Aim 1 studies and plan to screen an additional 58 women to account for screen failures for a total enrollment of 80 women to account for drop out. We believe that the difference between groups will likely be smaller given the clinical information (50% or less). We have chosen a difference of 20% in which to base our sample size calculations. We have consciously chosen not to enroll an adequately sized normal BMI group to detect the same amount of difference (20%) given that there are published PK/PD standards. We are utilizing this group to verify the accuracy of our findings under our environment, the targeted 10 total number of subjects (after 12 screening) in the control arm would achieve the 80% power to detect 47% difference in follicular rupture given the 73 of women taking UPA ECx1 using two-sided Z test with 2.5% significance level. The total number of subjects in the control arm was chosen as a convenience sample but this number of subjects should supply us with an adequate amount of data to ensure that our PK/PD results are similar to published values in a normal BMI cohort.

Protection of human subjects:

1. Risks to Subjects

Human Subjects Involvement and Characteristics

Reproductive-aged (18-35 year old), ovulatory, healthy women with a normal or obese BMI with no contraindications to the study medications and not at risk for or seeking pregnancy will constitute the target population for this study.

All enrollment and clinical evaluations will be performed at OHSU in Portland, Oregon. Serum samples will be prepared at OHSU and analyzed at the ONPRC Endocrine Core Laboratory under the direction of [name]. De-identified pharmacokinetic data will be analyzed by our consulting pharmacokinetic specialist, [name].

Sources of Materials

The sources of research material for the clinical portion of this proposal will be new specimens obtained purely for this research protocol. The study investigators and/or research assistants/nurses will perform all study procedures.

Potential Risks

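### The exploratory LNG ECx2 v UPA ECx2 chi-square assumes different women, but about 20 are expected in both groups, so its standard error is off unless the within-woman correlation is zero

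*Combined protocol and SAP*

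**What the plan says.** The analysis is in Part 2, Data Analysis & Sample Size, after the description of the PK parameters. The proportion of women with delayed rupture is compared across the four LNG and UPA regimens, with one named test: "between LNG ECx2 and UPA LNG ECx2 using Chi-square test". The second regimen is evidently UPA ECx2. A power above 80% for a 23-point difference at the 5% level is claimed "given the projected sample size (35 per group in Part 1 and 80 per group in Part 2").

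The same paragraph limits its ambition: "Due to exploratory purpose of these analyses, the analysis will be descriptive". It also says the comparison may help to guide later studies or even clinical management.

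Four other places bear on who is in the two groups:

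- Methods, Study design: "Eligible women can take part in both aspects of the study and in no particular order".
- Part 1 LNG-EC, on allocation: "Randomization will occur in a 1:1 fashion"; and on study end: "Subjects will have the option to undergo a washout cycle and participate in the studies detailed in Part 2".
- Part 2 UPA-EC, on the treatment cycles: "only the obese group will complete treatment cycle 2 and receive a double dose of UPA EC (60mg").
- Part 2 sample size: "We estimate that 40 women will choose to participate in Aim 2 after completing Aim 1 studies".

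The methods that allow for repeated women, McNemar's test and the GEE in Part 2, are stated only for UPA ECx1 against UPA ECx2.

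**The concern.** A two-sample chi-square takes the variance of the difference as the sum of two independent variances. If some women supply an outcome to both groups, a covariance term is missing. Its sign and size depend on how alike one woman's two responses are.

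What is at stake is the p-value of the only LNG v UPA test that the plan names. If the correlation is positive, the test rejects too rarely and gives up power that the shared women could provide. If it is negative, the false-positive rate is somewhat above 5%.

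**Working it through.** **Inputs from the plan.** Group sizes n1 = 35 and n2 = 80. Women expected to enter Part 2 after Part 1: 40. Part 1 allocation 1:1. Part 1 planning rates: 90% ovulate at the normal time on LNG ECx1, so 10% are inhibited; with the 30-point planning difference, about 40% on LNG ECx2.

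**Derived overlap.** m = 40 × 1/2 = 20 women in both groups: 20/35 = 57% of the LNG ECx2 group and 20/80 = 25% of the UPA ECx2 group. This assumes that entry into Part 2 does not depend on the LNG arm and that these women complete the UPA ECx2 cycle. Part 2 is described both as a randomised cross-over and as a fixed order of doses. Under either, every obese completer receives UPA ECx2, so m does not change.

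**Assumed.** The within-woman correlation (rho) is not in the documents. A range of -0.2 to 0.6 is shown.

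**The plan's own power figure.** No base rate is given, so the figure cannot be reproduced as a single value. For 35 v 80, a 23-point difference and a two-sided 5% test with pooled variance, power runs from about 63% to 96% over possible base rates. It is 63% at 40% v 63%. This spread exists without any overlap.

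**Variance and size.** With a common rate p and q = 1 - p:

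- assumed variance = pq(1/n1 + 1/n2)
- true variance = pq(1/n1 + 1/n2) - 2·m·rho·pq/(n1·n2)
- ratio true/assumed = 1 - 2·rho·m/(n1 + n2) = 1 - 40·rho/115
- true size of the nominal 5% test = 2·(1 - Φ(1.96/√ratio))

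| rho | ratio | √ratio (SE true/assumed) | size, m = 20 | size, m = 15 to 25 |
|---|---|---|---|---|
| -0.2 | 1.070 | 1.034 | 5.8% | 5.6 to 6.0% |
| 0 | 1 | 1 | 5.0% | 5.0% |
| 0.2 | 0.930 | 0.965 | 4.2% | 4.4 to 4.0% |
| 0.4 | 0.861 | 0.928 | 3.5% | 3.8 to 3.1% |
| 0.6 | 0.791 | 0.890 | 2.8% | 3.3 to 2.3% |

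With the completer targets, 31 (= 62/2) v 73, m falls to about 16 (20 × 31/35 × 73/80) to 18 (20 × 31/35). Sizes are then 5.7 to 5.8, 5.0, 4.3 to 4.2, 3.6 to 3.5 and 3.0 to 2.8%.

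**Is -0.2 possible?** For a common rate p below one half, the lowest attainable correlation is -p/(1 - p). At 10% that is -0.1/0.9 = -0.11, so the 5.8% cannot occur there. At 40% it is -0.67, so -0.2 is attainable.

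**Power of the alternatives.** Score-type test: z = (p1 - p2)/√[p(1 - p)(1/n1 + 1/n2) - 2S/(n1·n2)], where p is the pooled proportion and S is the sum over shared women of (x - p1)(y - p2). Simulation used correlated binary pairs, 35/80/20, with 200,000 replicates for the score and chi-square tests. The GEE is logistic, clustered on woman, with a Wald test.

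| 40% v 63% | rho 0 | rho 0.2 | rho 0.4 |
|---|---|---|---|
| Chi-square | 63.0% | 63.5% | 63.8% |
| Score-type | 63.6% | 66.8% | 70.1% |
| GEE Wald | 62.9% | 66.3% | 69.5% |

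At rho -0.2 the score test has 60.8% against 62.5% for chi-square. Its size is 4.4 to 5.3% at common rates of 10 to 50%. The GEE Wald test's size at 40% in both groups is 4.7 to 5.0%.

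At 10% v 33% and rho 0.2 / 0.4, the score test has 82.4 / 85.6%, chi-square 80.1 / 81.1% and GEE Wald 77.9 / 81.5%, with 2.5% of the GEE fits unusable. At 10% in both groups the Wald test's size is only 2.5 to 3.1%.

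**The case against.** The strongest reply is that little depends on this. The plan calls the comparison exploratory and descriptive, and the likelier error is conservative, so it would not produce excess false positives. The size of the error also rests on a correlation that the documents do not give and on an overlap that is derived. All of that stands, and it sets the low weight. It does not remove the point, because the plan still names a test, a significance level and a power for this contrast.

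A second reply is that the remedy gains little. In some settings it loses: at 10% v 33% with 31 v 73 and 16 shared, the score test differs from chi-square by -3.3, -1.2 and +1.0 points of power at rho -0.2, 0 and 0.2. That is a fair cost to state.

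A reader might go further and infer any of three things that the documents do not support:

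- **That the overlap makes the test generally liberal.** It does so only for negative correlation, and at a common 10% rate even -0.2 is impossible.
- **That the overlap explains a shortfall from the stated power.** It does not lower the chi-square's power for positive correlation (63.0% at rho 0, 63.8% at 0.4). Whether 80% is reached depends on the unstated base rate, which is a separate matter.
- **That a logistic GEE Wald test should be ruled out.** Its poor behaviour appears near a 10% rate. The plan's 10% belongs to LNG ECx1, which is not in this contrast. At the roughly 40% implied for LNG ECx2 it is within 1 point of the score test.

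**Conclusion.** The point holds, at low severity. The plan applies an independent-groups test to two groups that, by its own estimate of 40 women continuing, would share about 20. At any non-zero within-woman correlation the standard error is wrong: about 4% too large at 0.2 (1/0.965) and 8% too large at 0.4 (1/0.928), or about 3% too small at -0.2. In terms of size, the nominal 5% becomes roughly 3 to 4% for correlations of 0.2 to 0.6, and at most about 6% at -0.2.

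That positive correlation is likelier is a judgement that the same woman tends to respond alike in two cycles; the documents do not say so. The estimated proportions, the Part 1 chi-square and the Part 2 McNemar test are untouched.

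Two related gaps are separate points of missing detail. The plan does not say how repeated women are handled in the cross-regimen survival analysis. It also gives no single definition of delay for all four regimens: the Part 1 endpoint is no rupture, and the Part 2 endpoint is a delay of at least 6 days.

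**What to change.** In the exploratory comparison paragraph of Part 2, Data Analysis & Sample Size, replace the chi-square for LNG ECx2 v UPA ECx2 by a method that accounts for women in both groups. Use either the two-proportion score-type test above, with twice the within-woman covariance term subtracted from the pooled variance, or a GEE clustered on woman. Either suits rates near 40%. If either regimen's rate is near 10%, prefer the score form, because the logistic GEE Wald test is conservative there and can fail to fit. Leave McNemar's test and the existing GEE for UPA ECx1 v ECx2 as planned.

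The cost is a change of wording, minor programming and linkage of each woman's Part 1 and Part 2 records. Compared with chi-square, the score test gives up as much as about 1 point of power at zero correlation, and about 2 to 3 points if the correlation is -0.2.
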